### 11.3 Graphical presentations

The following plots will be presented:

- Bar charts

### 11.4 Statistical tests employed

The following methods are employed in this study:

- Generalized mixed model
- Wilcoxon signed rank test

---

**For primary endpoint:**

The primary endpoint of the investigation is the change from baseline in IELT with the 5% Benzocaine condom versus the standard NRL condom, over a 4-week assessment period. For each subject, a mean IELT will be calculated across all intercourse episodes within a study period (baseline, assessment period 1, assessment period 2 and assessment period 3) and used for analysis.

For the calculation of the respective mean values, only IELT data points that were generated during a condom-based clinical-failure-free sexual intercourse are taken into account. Ejaculation is to be considered the posterior threshold.

If an IELT value is not considered valid due to the regulation listed in table 19.6 located in the appendix, it is not used in the calculation and is formally considered non-existent in the primary and secondary analyses. This value is also not considered further in any descriptive analysis.

Consequently, the classification of some values as "non-valid" can affect the categorization of the FAS and PP analysis population, as excluded IELT values cannot be evaluated in this consideration either.

The change from baseline in IELT will be analysed using a linear mixed model using data from all three condom groups, with the primary comparison between the 5% benzocaine condom with the standard NRL condom. The model will include fixed effects for treatment and period, a covariate for baseline IELT, and a subject as a random effect. The differences between the 5% benzocaine condom and the standard NRL condom will be presented with a 95% CI and an associated p-value. Statistical significance will be assessed at the two-sided 5% level. No adjustment for multiplicity will be made since there is a single primary comparison (5% benzocaine condom versus standard NRL condom). No assumptions of normality will be checked based on utilizing the Generalized Linear Mixed Model (GLMM) to analyze the primary endpoint. If the model can't handle the violation, a non-parametric model will be used in the worst-case scenario, such as Wilcoxon signed ranks test with Hodges Lehmann estimator for treatment differences.

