##### Other variables

- Start date and time of intercourse [dd.mm.yyyy – hh:mm] + [single choice check box]
  - Date and time
  - The intercourse did not proceed
    - Specification why not proceed
- Report of condom breakage and condom slippage during the vaginal intercourse or withdrawal from the vagina.[multiple choice check box]
  - Condom broke
  - Condom completely slipped off from the base of the penis during intercourse
  - Condom completely slipped off from the base of the penis during withdrawal from the vagina
    - Hold on to the base of the condom during withdrawal from the vagina [yes/no]
  - No condom breakage or complete condom slippage
- Reaction to condom breakage or complete condom slippage [single choice check box]
  - Removed condom and carried on without a condom
  - Did not proceed further with intercourse.
  - Not applicable since the condom did not break or completely slip
- Usage of lubricant [single choice check box]
  - Yes, the investigation lubricant was used
  - Yes, another type of lubricant was used
    - Specification of other

- No
- Date and time of completing this IELT diary [dd.mm.yyyy – hh:mm]

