**Other variables**

3. Did you experience a numbing sensation following application and during use of this condom?  
[Yes/No]

4. How did you like the numbing effect of the condom? (for completion only if answer yes to the above question 3)

- Too little for me

- Slightly too little for me
  - Just about right
  - Slightly too much for me
  - Too much for me
5. How fast did you feel the numbing effect of the condom after putting it on? (for completion only if answer yes to the above question 3)
- Immediately
  - Within seconds
  - After ten seconds to about half a minute
  - After more than a half a minute
  - Not at all
6. On what area(s) on your penis could you feel the numbing effect? See the diagram below for illustration (for completion only if answer yes to question 3)
- Tip of the penis
  - Shaft of the penis
  - Base of the penis
  - None of these

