### Notes from table:

1. Condom broke during the vaginal intercourse or withdrawal from the vagina.
2. Condom completely slipped off from the base of the penis during intercourse.
3. Condom completely slipped off from the base of the penis during withdrawal from the vagina.
4. Condom completely slipped off from the base of the penis during withdrawal from the vagina due to not holding on to the base of the condom during withdrawal from the vagina.
5. A logical discrepancy arises between the individual parameters queried for clinical failure and the simultaneous exclusion of a clinical failure. In this case, the worst-case scenario is assumed, which implies a clinical failure of the condom.
6. The study objective is IELT duration, not clinical failure. If this parameter is missing/not ticked, it can be assumed there is no breakage or slippage and the IELT is considered to be valid. No further imputation of the question is carried out.
7. The slippage is after intravaginal ejaculation so the IELT can be used.

[figure not shown]
---

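### The SAP admits only condom-based, failure-free acts, but Table 19.6 applies only the failure half, so an act finished without the condom and with no failure recorded counts as valid for that condom

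*SAP*

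**What the plan says.** SAP 11.4 (primary endpoint) sets two conditions for an IELT value to enter a period mean, condom-based and failure-free: "only IELT data points that were generated during a condom-based clinical-failure-free sexual intercourse are taken into account". It adds a time limit: "Ejaculation is to be considered the posterior threshold". The rule is applied through the appendix: "If an IELT value is not considered valid due to the regulation listed in table 19.6 located in the appendix", the value is dropped from every analysis and can also affect membership of the FAS and PP sets.

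The assessment-period diary variables in SAP 9.1 cover breakage, slippage during intercourse ("Condom completely slipped off from the base of the penis during intercourse"), slippage at withdrawal, and a box for none of these. A separate single-choice item asks how the couple reacted to a failure. One answer is "Removed condom and carried on without a condom"; the answer for an act with no failure is "Not applicable since the condom did not break or completely slip".

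Table 19.6 has columns for breakage, the slippage types and the no-failure box. It has none for the reaction item and none for condom wear. Its note 6 says that if the no-failure box is left blank, "it can be assumed there is no breakage or slippage and the IELT is considered to be valid".

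Protocol 6.3 instructs subjects to use one investigational condom per act and mentions continuing without it only after breakage or slippage. Protocol 6.10.1 defines the diary record per condom use.

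**The concern.** The first of the two conditions cannot be checked from the listed data. A man may remove the condom before ejaculation without a failure, or time an act without the study condom. He has no failure to tick, and his IELT is averaged into that condom's mean. If he leaves the failure boxes blank but ticks that he removed the condom and carried on, the value is still kept.

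Such acts are plausible in this population. Under inclusion criterion 9 the partner already uses non-barrier contraception or is post-menopausal. Exclusion criterion 19 removes couples who need condoms for protection against a specific infection. The subject questionnaire also allows for numbing that is too strong ("How did you like the numbing effect of the condom").

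At stake is the meaning of the primary mean: IELT with a given condom on until ejaculation. These acts could also count towards the four recorded uses that the PP set requires in a period (SAP 8). SAP Amendment 1 was written to define which IELT values are usable, so an unworkable condition defeats part of its purpose.

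**Working it through.** **1. Set the diary items against Table 19.6.** The four failure flags give 16 combinations. Table 19.6 excludes 12: 8 with breakage, and 4 without breakage but with slippage during intercourse. It uses 4: 3 with slippage at withdrawal only, which note 7 places after ejaculation, and 1 with no failure. Table 19.6 thus handles the failure half of the rule as intended. By type of act:

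| How the act ended | What the listed items record | Table 19.6 result |
|---|---|---|
| Breakage or slippage during intercourse reported, continued without condom | Failure box and reaction box | Not used |
| Slippage at withdrawal only | Withdrawal box | Used |
| Condom removed by choice before ejaculation, no failure | Nothing; the reaction item fits as not applicable | Used |
| Act timed without the study condom | Nothing | Used |
| Failure boxes blank, reaction box says removed and carried on | A contradiction | Used, whether or not the no-failure box is ticked |

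The last three rows fail the condom-based condition, or appear to, and are still used. In the last row the information is already collected but not consulted. Note 5 resolves a different contradiction, a failure box ticked together with the no-failure box, by assuming the worst case. Here the result goes the other way.

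**2. Reproduce the plan's sample size (SAP 12.7).** Inputs: SD 7.1 min, correlation 0.5, difference 2 min, two-sided 5%, 90% power, paired t-test, 10% dropout.

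- SD of the difference = 7.1 × √(2 × (1 − 0.5)) = 7.1 min.
- The noncentral t distribution gives n = 135, with power 90.1%.
- 135 / (1 − 0.10) = 150.

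Both figures match the SAP.

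**3. Illustrate the size.** The documents give no rate for such acts, so f is assumed. Suppose that, on average, a share f of each subject's Test Condom A acts has the control mean and the SD of the difference stays 7.1. The expected difference is then 2(1 − f). Power at n = 135:

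| f | Difference (min) | Power |
|---|---|---|
| 0% | 2.00 | 90.1% |
| 2% | 1.96 | 89.0% |
| 5% | 1.90 | 87.0% |
| 10% | 1.80 | 83.3% |
| 20% | 1.60 | 73.9% |

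The assumption of control-like behaviour is a convenience. The control is itself sex with a condom, and benzocaine already applied may go on acting after removal.

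**The case against.** The strongest reply is that the one route the protocol describes, continuing after a breakage or slippage, is captured when reported and excluded. What is left is a protocol deviation with several controls on it:

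- the instruction to use one condom per act and a diary kept per condom use (protocol 6.3 and 6.10.1);
- the visit question on adherence to the rules, with a free-text reason, and the count of condoms used at product return (SAP 9.3);
- PP exclusions decided before database lock (SAP 8).

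This stands in part. The count can expose acts with no condom. None of these controls is designed to detect removal during an act, and none feeds Table 19.6.

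The diary form is also not in the documents. The translations list in SAP 9.1, headed for baseline and all three assessment periods, includes a condom name and brand, which implies a further yes/no question. It may belong to baseline only, where protocol 7.2 has couples report use of a commercial condom. Even if it applies throughout, a brand name does not show wear until ejaculation, and Table 19.6 does not use it.

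A further objection is that removal because of numbing is a treatment-related event after randomisation, so excluding those acts favours acts that were tolerated. That is fair, and it is why the fix includes a run with them kept.

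A reader might infer three stronger things that the documents do not support:

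- **Every act finished without the condom counts as valid.** Table 19.6 excludes those with a reported breakage or slippage during intercourse.
- **The gap hides poor tolerability.** Numbing, comfort, erection, tolerability satisfaction and adverse events are all collected apart from IELT validity.
- **The effect is certainly diluted.** Residual benzocaine may act after removal, and discomfort or loss of erection can prompt removal of any condom, the control included.

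**Conclusion.** The point holds in a limited form. SAP 11.4 states a two-part rule and Table 19.6 applies one part. Acts finished without the study condom and with no failure recorded are kept as valid, and in one situation they are kept although a collected answer says the condom was removed.

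The frequency and direction of bias are unknown. Under the control-like assumption the loss is small at low rates (about 1 point of power at f = 2%, 3 points at 5%) and about 7 points at 10%. These figures illustrate scale and do not estimate bias. The finding rests on the variables listed in the SAP and would change if the actual diary form has a wear item. It merits correction because the condition is the sponsor's own and making it workable is cheap.

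**What to change.** 1. **Use the reaction item in Table 19.6.** If the subject ticked that he removed the condom and carried on, but ticked no failure, extend the worst-case principle of note 5 to that entry and do not use the IELT. This needs no new data and covers pages already completed.
2. **Add one diary item for the assessment periods**, such as *Study condom worn from entry until ejaculation: yes/no*, with a matching Table 19.6 column in which *no* means not condom-based and IELT not used. Confine it to the assessment periods, because condom use at baseline is conditional under protocol 7.2.
3. **Tabulate the affected acts by condom and repeat the primary model with them included**, because removal may be related to treatment.

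The cost is a short SAP amendment, a new diary version with whatever ethics notification that requires, one table column, one tabulation and one sensitivity run. Pages completed before the change will lack the new item. For those, comparing IELT records with condoms used can flag acts with no condom but not removal during an act.

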**For secondary endpoints**

All secondary endpoints will be evaluated based on comparing the 5% and 3% benzocaine condoms with the standard NRL condom. No adjustment for multiplicity is planned for the secondary endpoints, and so p-values will be interpreted with appropriate consideration of Type I error.

The secondary endpoints of the investigation are:

Change from baseline in IELT with the 3% Benzocaine condom compared to the standard NRL Condom, over a 4-week assessment period.

Proportion of subjects who achieve an increase of 2, 3, 4 mins from baseline in IELT in the 5% and 3% benzocaine condoms compared to the standard NRL Condom.

- The change from baseline IELT with the 3% benzocaine condom compared to the standard NRL condom will be evaluated using the same linear mixed model as for the primary endpoint. The difference in least square means and associated 95% CI will be calculated, with a p-value to assess statistical significance.
- The proportion of subjects who achieve an increase of 2, 3 or 4 mins from baseline in IELT (calculated from the mean across all intercourse episodes within a period) will be calculated

for each condom type. The proportion achieving an increase of 2, 3 or 4 mins will be compared for the 5% and 3% benzocaine condoms versus the standard NRL condom using a GLMM with marginal means under the assumption that the mean of the outcome variable (1=success or 0=failure) follows a binomial distribution. Factors in the model will include fixed effects for treatment and period, and baseline IELT as a covariate. Subject will be included as a random effect. Comparison between the 5% and 3% Benzocaine condoms with the standard NRL condom will be expressed as an odds ratio, with an associated 95% CI and p-value.

A measure of Patient Global Impression of Change (PGIC) at the end of each 4-week assessment period, in subjects using the 5% and 3% benzocaine condoms compared to the standard NRL Condom.

- The PGIC recorded at the end of each condom assessment period will be summarised by condom type, as the number and percentage in each category of the PGIC (Very much better, Better, Little better, No change, Little worse, Worse, Very much worse). A comparison of the PGIC in each of the 5% and 3% Benzocaine condoms versus the standard NRL condom will be performed using a GLMM, assuming a multinomial distribution for the response variable. Factors in the model will include fixed effects for treatment and period. Subject will be included as a random effect. Comparison between the 5% and 3% Benzocaine condoms with the standard NRL condom will be expressed as an odds ratio, with an associated 95% CI and p-value. In the event that some categories of the PGIC have too few subjects for the model to fit, the number of categories in the PGIC responses may be reduced (e.g., better, no change, worse) for purposes of analysis.

A measure of EMSEX pleasure scale at the end of each 4-week assessment period, in subjects using the 5% and 3% benzocaine condoms compared to the standard NRL Condom.

- After each coital act, the mean of the responses on the EMSEX pleasure scale (0 to 100) will be calculated as the sum of responses divided by number of questions answered. For each condom assessment period, a subject-level mean EMSEX pleasure scale will then be derived using data from all coital acts. The EMSEX pleasure scale score will be analysed using a linear mixed model using data from all three condom groups, with comparisons between the 5% and 3% Benzocaine condoms with the standard NRL condom. The model will include fixed effects for treatment and period, and subject as a random effect. The between group differences will be presented with a 95% CI and an associated p-value.

User acceptability, experience and preference of each condom type will be evaluated through subject perceived questions, asked at the end of each 4-week assessment period.

- Responses to SPQs will be summarised for each condom type using descriptive statistics.

The in-use tolerability of each condom type will be evaluated through subject perceived questions, asked at the end of each 4-week assessment period.

A measure of the total clinical failure rate (in percent) of Test Condom A, Test Condom B and Control NRL condom, where as a failure is defined if at least one of the following variables are met (specified according to the high level definition of ISO-29943-1):

- 1.) Condom breakage or tearing of the condom during intercourse or withdrawal from the vagina
- 2.) Condom completely slipped off from the base of the penis during intercourse
- 3.) Condom completely slipped off from the base of the penis during withdrawal from the vagina because user did not hold onto the condom at the base of the penis during withdrawal.

Overall proportion of subjects with Adverse Events/ Adverse Device Effects (AEs/ ADEs), i.e., the occurrence of one or more AEs/ ADEs per subject.

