## 9.5.2 Secondary Endpoint(s)

All secondary endpoints will be evaluated based on comparing the 5% and 3% benzocaine condoms with the standard NRL condom. No adjustment for multiplicity is planned for the secondary endpoints, and so p-values will be interpreted with appropriate consideration of Type I error.

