### 9.5.2.1 Secondary Endpoint Analyses

The secondary endpoints of the investigation are:

- Change from baseline in IELT with the 3% Benzocaine condom compared to the standard NRL Condom, over a 4-week assessment period.
- Proportion of subjects who achieve an increase of 2 mins from baseline in IELT in the 5% and 3% benzocaine condoms compared to the standard NRL Condom.
- Proportion of subjects who achieve an increase of 3 mins from baseline in IELT in the 5% and 3% benzocaine condoms compared to the standard NRL Condom.
- Proportion of subjects who achieve an increase of 4 mins from baseline in IELT in the 5% and 3% benzocaine condoms compared to the standard NRL Condom.
- A measure of Patient Global Impression of Change (PGIC) at the end of each 4-week assessment period, in subjects using the 5% and 3% benzocaine condoms compared to the standard NRL Condom.
- A measure of EMSEX pleasure scale at the end of each 4-week assessment period, in subjects using the 5% and 3% benzocaine condoms compared to the standard NRL Condom.
- User acceptability, experience and preference of each condom type will be evaluated through subject perceived questions, asked at the end of each 4-week assessment period.

	Clinical Investigation Plan		
	Investigation No: 5078401	Protocol Version: V2.0 08-Jun-2023	Page 54 of 62

- The in-use tolerability of each condom type will be evaluated through subject perceived questions, asked at the end of each 4-week assessment period.
- A measure of the total clinical failure rate of Test Condom A, Test Condom B and Control NRL condom.
- Overall proportion of subjects with Adverse Events/ Adverse Device Effects (AEs/ ADEs), i.e. the occurrence of one or more AEs/ ADEs per subject.

The change from baseline IELT with the 3% benzocaine condom compared to the standard NRL condom will be evaluated using the same linear mixed model as for the primary endpoint. The difference in least square means and associated 95% CI will be calculated, with a p-value to assess statistical significance.

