## 12.6 Multiplicity

No adjustment for multiplicity will be made since there is a single primary comparison between the 5% benzocaine condom versus standard NRL condom.

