## 17 Topline results

The topline results include:

- Allocation of subjects in the respective study populations (SP, FAS, PP)
- Statistical analysis of the primary endpoint (FAS and PP)
- Selection of secondary efficacy endpoint(s) to support the primary endpoint (FAS and PP\*)
  - Change from baseline in IELT with the 3% Benzocaine condom compared to the standard NRL Condom
  - Proportion of subjects who achieve an increase of 2 mins from baseline in IELT in the 3% benzocaine condoms compared to the standard NRL condom.
  - Proportion of subjects who achieve an increase of 3 mins from baseline in IELT in the 3% benzocaine condoms compared to the standard NRL condom.
  - Proportion of subjects who achieve an increase of 4 mins from baseline in IELT in the 3% benzocaine condoms compared to the standard NRL condom.
  - Proportion of subjects who achieve an increase of 2 mins from baseline in IELT in the 5% benzocaine condoms compared to the standard NRL condom.
  - Proportion of subjects who achieve an increase of 3 mins from baseline in IELT in the 5% benzocaine condoms compared to the standard NRL condom.
  - Proportion of subjects who achieved an increase of 4 mins from baseline in IELT in the 5% benzocaine condoms compared to the standard NRL condom.
- Counts and percentages of (S)AEs (SP)
- Description of events in conjunction with causality to the study, pattern, intensity and outcome of (S)AEs (SP)

\* Provided that the rule for sensitivity analysis from chapter 12.2 applies.

---

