## Overview

The summary of the statistical analysis scheme is presented in the following table:

Target variables	Population	Graphs	Statistical methods
Disposition of subjects	SP	Flowchart	
Disposition of investigational products	SP	Flowchart	
Baseline characteristics	SP		
childbearing potential, ethnicity, physical examination	SP	--	Counts and percentages
Age, height, weight, BMI	SP	--	Descriptive statistics
Medical history	SP	--	Counts and percentages
Primary variable*	FAS*, PP**		
IELT with the 5% Benzocaine condom A		Bar chart	Descriptive statistics 95 % Confidence Intervals GLMM or Wilcoxon signed ranks test
Secondary variable(s)	FAS		
IELT with the 3% Benzocaine condom B	FAS**, PP**	Bar chart	Descriptive statistics 95 % Confidence Intervals GLMM or Wilcoxon signed ranks test
EMSEX Pleasure Scale for Test Condom A OR B against standard NRL condom	FAS**	--	Descriptive statistics 95 % Confidence Intervals GLMM or Wilcoxon signed ranks test
Patient Global Impression of Change (PGIC)	FAS**	--	Counts and percentages GLMM or Wilcoxon signed ranks test 95 % Confidence Intervals
Subject perceived questions	FAS**		Counts and percentages

Target variables	Population	Graphs	Statistical methods
Proportion of subjects who achieve an increase of 2 mins from baseline in IELT	FAS**, PP***	--	Descriptive statistics Counts and percentages GLMM or Wilcoxon signed ranks test 95 % Confidence Intervals
Proportion of subjects who achieve an increase of 3 mins from baseline in IELT	FAS**, PP***	--	
Proportion of subjects who achieve an increase of 4 mins from baseline in IELT	FAS**, PP***	--	
Total clinical failure rate	FAS**	--	Descriptive statistics Counts and percentages

\*: Confirmatory hypothesis testing

\*\*: No confirmatory hypothesis testing, part of secondary analysis

\*\*\*: Provided that the rule for sensitivity analysis from chapter 12.2 applies.

Additional tables and figures are acceptable for illustrative purposes. Additional statistical tests can be performed, if reasons are given in the final report. The corresponding p-values have to be interpreted purely descriptive in the context of an explorative data analysis.

Examples of crucial tables, listings and figures can be seen in Chapter 19.

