**Mock table for results of GLMM for product comparisons**

Results of generalised linear mixed modell for product comparison (FAS or PP)						
Parameter	Level of categorial parameter	Regression coefficient	SE	DF	t-value	p-value
Intercept		XX.X	XX.XX	XX	XX.X	X.XXXX
Parameter 1		XX.X	XX.XX	XX	XX.X	X.XXXX
Parameter 2	Parameter 2 - Level 1	XX.X	XX.XX	XX	XX.X	X.XXXX
Parameter 2	Parameter 2 - Level 2	XX.X	XX.XX	XX	XX.X	X.XXXX
Parameter 2	Parameter 2 - Level 3	0 (Reference)				
Parameter 3		XX.X	XX.XX	XX	XX.X	X.XXXX

Note on the result: **bold p-Value: significant (p ≤ 0.05)**

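### The first secondary objective, effectiveness of the 3% condom on IELT, has no error-controlled test, and the documents label its p-value inconsistently; a fixed sequence after the primary would settle both.

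*SAP*

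**What the plan says.** **Primary.** SAP 11.4 (For primary endpoint) names one primary comparison, 5% condom against control on change from baseline in IELT, and states "Statistical significance will be assessed at the two-sided 5% level". The success criteria (Protocol synopsis and 2.2) name Test Condom A only.

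**Multiplicity.** SAP 12.6 reads "No adjustment for multiplicity will be made since there is a single primary comparison between the 5% benzocaine condom versus standard NRL condom". For the secondaries, Protocol 9.5.2 (repeated in SAP 11.4) adds "No adjustment for multiplicity is planned for the secondary endpoints, and so p-values will be interpreted with appropriate consideration of Type I error". There is no hierarchy and no allocation of alpha.

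**The 3% IELT comparison.**
- SAP 11.4 estimates it from the primary model and states "The difference in least square means and associated 95% CI will be calculated, with a p-value to assess statistical significance"; Protocol 9.5.2.1 has the same sentence, ending "with a p-value to assess statistical significance".
- The SAP Overview marks it "No confirmatory hypothesis testing, part of secondary analysis". Planned Table 14.2.2.3 carries the equivalent footnote for both FAS and PP.
- Figures 14.2.2.1 and 14.2.2.2, which show the 3% condom and control, are captioned as figures for the primary hypothesis.

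**The other ten secondary tests** (responders at 2, 3 and 4 minutes, PGIC and EMSEX, each for both condoms) get 95% confidence intervals and p-values. The Overview marks them non-confirmatory. The planned tables do not repeat that mark: the double asterisk on the responder tables concerns only when a PP analysis is run, and the PGIC and EMSEX tables have no mark. The mock GLMM table carries the note "bold p-Value: significant (p ≤ 0.05", as does the mock odds-ratio table. SAP 17 puts the 3% IELT test and the six responder tests in the topline under "Selection of secondary efficacy endpoint(s) to support the primary endpoint".

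**The concern.** The 3% condom is a different product from the 5% condom, and determining its effectiveness is the first secondary objective. A reader of the results will want to know whether a small p-value for 3% against control establishes that effect. The Overview and Table 14.2.2.3 say it does not. The analysis text, the bolding note and the two figure captions use the language of a formal test. The instruction to consider Type I error is sensible, but it is not a rule for when a p-value supports a claim. The reason given in SAP 12.6, a single primary comparison, does not extend to a significance statement about a second condom.

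Two things are at stake. A strong 3% result could not be called confirmed, although a confirmatory test could be had at no cost to the primary. And the mixed labels leave room for argument, once results are known, about how much the 3% p-value means.

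**Working it through.** **1. The plan's own sample size.** Inputs from Protocol 3.3 and SAP 12.7: SD 7.1 minutes, within-subject correlation 0.5, difference 2 minutes, two-sided 5%, paired t-test, 90% power, 10% dropout.
- SD of a paired difference = 7.1 × √(2 × (1 − 0.5)) = 7.1.
- The noncentral t calculation gives 135 completers (power 0.901); 135 / 0.9 = 150 randomised.

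The stated 135 and 150 are reproduced, so the two-sided 5% for the primary is consistent with its sizing.

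**2. Count of inferential secondary tests (SAP 11.4).** 3% IELT 1; responders 3 thresholds × 2 condoms = 6; PGIC 2; EMSEX 2. Total 1 + 6 + 2 + 2 = 11. The PGIC count assumes one odds ratio per condom, which the word multinomial does not guarantee. The topline subset is 1 + 6 = 7.

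**3. Error if either IELT result were claimed.** With equal variances and equal correlation ρ between periods, each contrast with control has variance 2σ²(1 − ρ), and the two contrasts have covariance σ²(1 − ρ) through the shared control. Their correlation is therefore 1/2 whatever ρ is. Under no effect of either condom, with each test at |z| > 1.96:

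| Correlation between the two tests | Chance of at least one false positive |
|---|---|
| 0 | 0.098 |
| 0.5 | 0.091 |
| 0.9 | 0.070 |

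A simulation of the three-period design (135 subjects, SD 7.1, correlation 0.5) gives 0.092.

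**4. Error under a fixed sequence.** Test 5% against control at 0.05, and test 3% against control at 0.05 only if the first is significant in favour of the 5% condom.
- If the 5% condom has no effect, any false claim needs the first test to reject: at most 0.05.
- If the 5% condom works, only the 3% claim can be false: at most 0.05.

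The family-wise rate for the two IELT tests is therefore at most 0.05, and the first test is unchanged. By comparison, splitting alpha equally (0.025 each) would lower primary power at 135 completers from 0.90 to 0.84.

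**5. Power for the 3% claim under the sequence.** Standard error = 7.1 / √135 = 0.611; assumed 5% effect 2 minutes, so expected z = 2 / 0.611 = 3.27; correlation between contrasts 0.5. The documents give no 3% effect, so the values below are assumptions.

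| Assumed 3% effect | Expected z | Tested alone | Within the sequence |
|---|---|---|---|
| 2.0 min | 3.27 | 0.91 | 0.84 |
| 1.5 min | 2.45 | 0.69 | 0.66 |

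These are normal approximations. Simulated t-tests give 0.83 and 0.65 within the sequence.

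**The case against.** The strongest reply is that the SAP has already decided. Its Overview reserves confirmatory testing for the primary variable. Table 14.2.2.3 is marked non-confirmatory, while the corresponding primary table leaves FAS unmarked. The success criterion is limited to Test Condom A, and the absence of adjustment for secondaries is disclosed in both documents. An unadjusted p-value reported as non-confirmatory is a coherent and common choice. The mock tables are generic templates, and a topline list that supports the primary fits a supportive role.

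Most of this stands. A reader might infer that all eleven secondary tests are run as significance tests at 5%. The documents do not support that: the significance phrase is attached to the 3% IELT comparison alone, and no alpha is stated for any secondary. The 5% level is inferred from the 95% intervals and the template note.

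A reader might also quote a false-positive rate of 30% across the eleven tests. That figure assumes no effect anywhere and an equal correlation of 0.5 (13% at 0.9, 43% if independent). It measures an any-of-eleven claim that the plan never makes. The 9% figure is limited in the same way. Nor is the primary inference affected.

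The reply does not remove the inconsistent wording for the 3% comparison. Nor does it give a reason to leave the first secondary objective without a controlled test when one is available at no cost to the primary.

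**Conclusion.** The point holds as a gap in the claim structure with inconsistent labelling, not as an error in the primary analysis. The primary test keeps its 5% error rate and about 90% power. On its clearest reading the plan offers no confirmatory 3% claim, so a fixed sequence gives up nothing confirmatory and adds an error-controlled test of the first secondary objective.

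The 9% against 5% comparison rests on no effect of either condom and equal correlation between periods, and applies only if success on either condom were claimed. The power figures rest on the plan's SD and correlation, a 2-minute 5% effect and assumed 3% effects. The change is worth making before database lock.

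**What to change.** **Preferred.** In Protocol 9.5.2 and SAP 11.4 and 12.6, state that 3% against control on change in IELT is a confirmatory secondary, tested at two-sided 5% only if the primary comparison is significant in favour of the 5% condom. Then:
- keep every other secondary p-value (responders, PGIC, EMSEX) non-confirmatory, as the Overview has it;
- remove the bold-for-significant note from those tables;
- correct the captions of Figures 14.2.2.1 and 14.2.2.2;
- align the footnotes in the Overview and in the planned tables of 14.2.1 and 14.2.2;
- if the change is made in the SAP alone, update SAP 15, which reports no changes from the clinical investigation plan.

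**Minimum, if the sponsor prefers to keep the 3% comparison non-confirmatory.** Delete the significance phrase from Protocol 9.5.2.1 and SAP 11.4, remove the bolding note from the 3% IELT table too, and make the same label corrections.

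**Cost.** Wording only, with no extra subjects, data or primary alpha. Protocol 9.1 allows documented changes before database lock, and SAP 10.2 places unblinding after it. Under the preferred route no confirmatory 3% claim is possible if the 5% comparison fails. Under either route the responder, PGIC and EMSEX results cannot be presented as statistically significant findings.
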